9.5. Pharmacokinetics

Pharmacokinetics is not relevant for this protocol.

9.6. Pharmacodynamics

Pharmacodynamic parameters are not evaluated in this study.

9.7. Genetics

Information regarding genetic/ pharmacogenetic (PGx) research is included in [Appendix 6](#). The IEC/IRB and, where required, the applicable regulatory agency must approve the PGx and genetic assessments before these can be conducted at the site. The approval(s) must be in writing and will clearly specify approval of the PGx and genetic assessments (i.e., approval of [Appendix 6](#)).

In some cases, approval of the PGx and genetic assessments can occur after approval is obtained for the rest of the study. If so, then the written approval will clearly indicate approval of the PGx and genetic assessments is being deferred and the study, except for PGx and genetic assessments, can be initiated. When PGx and genetic assessments will not be approved, then the approval for the rest of the study will clearly indicate this and therefore, PGx and genetic assessments will not be conducted.

9.8. Biomarkers

Biomarkers are not evaluated in this study.

9.9. Health Economics OR Medical Resource Utilization and Health Economics

Health Economics/Medical Resource Utilization and Health Economics parameters are not evaluated in this study.

10. STATISTICAL CONSIDERATIONS

10.1. Hypotheses

The primary objective of this study is to evaluate the efficacy of UMEC 62.5 mcg and UMEC 31.25 mcg compared with placebo in participants with not well controlled asthma over a 24 week treatment period. This is a superiority study to demonstrate the benefit of UMEC at two dosage strengths 62.5 mcg and 31.25 mcg when compared to Placebo in patients on background therapy of FF 100 mcg. The primary efficacy endpoint is the mean change from baseline in trough FEV₁ at Week 24.

The test for the primary efficacy endpoint is such that the null hypothesis is that there is no difference between treatment groups.

$$H_0: T_1 - T_2 = 0$$

The alternative hypothesis is that there is a difference between treatment groups.

$$H_1: T_1 - T_2 \neq 0$$

For the primary endpoint (and other lung function related efficacy endpoints), the primary treatment comparisons of interest are:

- UMEC 62.5mcg vs Placebo
- UMEC 31.25mcg vs Placebo

For each comparison test on the primary endpoint, the null hypothesis is there is no difference between treatment groups. The alternative hypothesis is there is a difference between treatment groups.

Therefore T_1 and T_2 for these endpoints are the mean changes from baseline for the UMEC therapy and placebo, respectively, as listed above.

Details on all pairwise treatment comparisons of interest are provided in Section [10.5.2](#).

10.2. Sample Size Determination

Sample size calculation is based on the primary efficacy endpoint of mean change from baseline in trough FEV₁ at the end of the 24-week treatment period.

A total of 384 randomized participants are required for this study, with 128 participants in each of the three double-blind treatment groups: UMEC 62.5mcg, UMEC 31.25mcg or Placebo. Assuming 10% missing data on spirometry at the end of the 24-week treatment period, due to early withdrawal from study, approximately 115 participants per treatment group will have trough FEV₁ available for the primary analysis. The standard deviation for the mean change from baseline in trough FEV₁ at the end of the 24-week treatment period is estimated to be 350mL based on two previous Tiotropium moderate asthma studies. The study design and population of this study aligns well with these two phase III, 24 week, randomised, double blind, placebo-controlled, parallel-group, active comparator studies of Tiotropium. In patients with moderate asthma on a background therapy of ICS the standard deviations in change from baseline trough FEV₁ at Week 24 ranged from 325 to 354mL; from this a SD estimate of 350 mL was chosen. This was estimated from a wide selection of studies, critically to minimise the risk of reduced power for the primary endpoint. The range of observed treatment differences across the Tiotropium treatment groups is 133 – 185mL, which supports the expectation that the treatment effect seen in a moderate asthma population is larger than in the more severe asthma population in study 205715 treated on a background of FF/VI. This is in line with data from GSK study 200699 which showed UMEC 62.5 mcg to be an effective dose. An average increase in change from baseline trough FEV₁ at Day 29 of 136 mL was observed in an asthma subset of patients treated with FF/UMEC (100/62.5) compared with FF (100 mcg) alone. The GSK phase III closed triple asthma study 205715, which this study supports, is in a more severe asthma population and conservatively assumes a SD estimate of 400mL.

Based on a true population difference of 130 mL, a sample size of 115 patients per treatment group has an estimated 80% power to observe statistical significance at the two sided 5% level, for each of the two primary comparisons of interest for each UMEC dose. Using the above assumptions the smallest observed effect predicted to result in a

[figure not shown]
statistically significant difference between treatment groups is 90.5 mL (minimum detectable difference).

No interim analysis is planned for this study.

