5.5. Dose Justification

The 200699 (IB, GlaxoSmithKline Document [2011N123107_03](#), / IB Supplement, GlaxoSmithKline Document [2016N284764_00](#)) data showed UMEC 62.5 mcg to be an effective dose; after 4 weeks of treatment in the subset of patients with a primary diagnosis of asthma, an average increase in change from baseline trough FEV1 at Day 29 of 136 mL was observed in those participants treated with FF/UMECA (100/62.5 mcg) compared to those participants treated with FF (100 mcg) alone. However, study 200699 did not assess the UMEC 31.25 mcg dose, therefore, the efficacy and safety profile of both 31.25 and 62.5 mcg doses will be assessed in this study when administered via a separate inhaler to participants treated on a background of FF 100 mcg. No safety signal was identified with any of the UMEC doses (15.6, 62.5, 125 and 250 mcg) evaluated in the 200699 study.

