10.5.3. Multiple Comparisons and Multiplicity

In order to account for multiple tests involving the two UMEC doses a step-down testing procedure will be applied whereby inference for a test in the pre-defined hierarchy is dependent upon statistical significance having been achieved for the previous test in the hierarchy.

A step-down procedure with the following hierarchy will be used for the primary comparisons in the primary endpoint.

- The contrast between UMEC 62.5 mcg vs Placebo
(two-sided, alpha = 0.05. Null hypothesis of no treatment difference)
- The contrast between UMEC 31.25 mcg vs Placebo
(two-sided, alpha = 0.05. Null hypothesis of no treatment difference)

The second hypothesis will be formally tested only if the first hypothesis has been rejected, thus maintaining the overall significance level at 5%.

Specifically, if the defined treatment comparison for the primary efficacy endpoint at the highest dose of UMEC 62.5 mcg is significant at 0.05 level then the efficacy of UMEC 62.5 mcg is demonstrated, and the treatment comparison can be repeated on the UMEC 31.25 mcg dose.

Note that, in the event that the first hypothesis is not rejected a nominal p-value for the second hypothesis may be provided in the displays for descriptive purposes only and will not alter the conclusion of the step-down procedure.

No multiplicity adjustment will be made on these two treatment comparisons on the secondary endpoint.

For all efficacy endpoints (primary, secondary and other), treatment comparisons between UMEC 62.5 vs UMEC 31.25 mcg informally investigating the benefit of increasing UMEC dose will be made without adjusting for multiplicity. Any p-values ≤ 0.05 will be identified as nominally significant.

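### The 80% power stated for each primary comparison does not apply to UMEC 31.25 mcg under the step-down test, where it is about 69%

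*Protocol*

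**What the plan says.** Section 10.2 sizes the trial on the Week 24 change from baseline in trough FEV1. It takes one true difference for both doses: "Based on a true population difference of 130 mL, a sample size of 115 patients per treatment group". On the variability it says: "from this a SD estimate of 350 mL was chosen". With 128 randomized per arm and 10% missing data, it expects that "approximately 115 participants per treatment group will have trough FEV₁ available for the primary analysis". From these inputs it claims "80% power to observe statistical significance at the two sided 5% level, for each of the two primary comparisons of interest". The sensitivity table in Section 10.3 varies one treatment difference and one SD at a fixed 115 per arm.

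Section 10.5.3 sets a fixed order, 62.5 mcg against placebo and then 31.25 mcg against placebo, each at two-sided 0.05: "The second hypothesis will be formally tested only if the first hypothesis has been rejected, thus maintaining the overall significance level at 5" per cent. If the first test fails, the second p-value may be shown but is descriptive and cannot change the conclusion.

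On prior evidence for the lower dose, Section 5.5 notes that "study 200699 did not assess the UMEC 31.25 mcg dose".

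**The concern.** The power claim and the testing rule do not describe the same test for the lower dose. Section 10.2 treats the two comparisons as equal and free-standing. Under Section 10.5.3 a formal success for 31.25 mcg requires significance for 62.5 mcg as well, so its power is a joint probability and must be lower than the power of its own comparison. Neither Section 10.2 nor Section 10.3 gives a power under the hierarchy or labels the 80% as unadjusted for it.

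Both comparisons are primary, and Section 10.1 describes a superiority trial meant to show benefit at both strengths. A reader of Section 10.2 would put the risk of missing the lower-dose claim at 20%. That understates the risk even if half the dose works exactly as well.

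**Working it through.** **Inputs.** From Section 10.2: difference 130 mL for each dose, SD 350 mL, 115 evaluable per arm (128 × 0.9 = 115.2), two-sided 5% level. From Section 7.3: 1:1:1 allocation. From Section 10.5.3: the test order and the gate.

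**Reproducing the stated figure.**
- Standard error of a difference: 350 × √(2/115) = 46.16 mL.
- Standardized effect: 130 / 46.16 = 2.817.
- Single-comparison power: Φ(2.817 − 1.960) = Φ(0.857) = 0.804. The noncentral t with 228 df gives 0.801.
- Smallest significant difference: 1.960 × 46.16 = 90.5 mL, as stated in Section 10.2.
- The 15 cells of the Section 10.3 table agree with a single two-sample t-test to within about 0.005.

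The 80%, and every entry in the table, is therefore the power of one comparison taken alone.

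**Correlation of the two tests.** Both differences subtract the same placebo mean. Their covariance is σ²/n and each variance is 2σ²/n, so the correlation is 0.5. The protocol does not state this value; it follows from the shared arm, equal n and a common SD.

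**Power for 31.25 mcg under the step-down.** This is the bivariate normal probability, with correlation 0.5, that both statistics exceed 1.960:

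P(Z₁ > 1.960 and Z₂ > 1.960) = Φ₂(0.857, 0.857; 0.5) = **0.693**.

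A simulation of 400,000 trials with t-tests gives 0.688 with pairwise variances and 0.690 with the variance pooled over three arms. Treating the tests as independent would give 0.804² = 0.647, which is wrong here because of the shared placebo.

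**Where the 31% comes from.**
- 62.5 mcg not significant, so the gate stays closed: 1 − 0.804 = 0.196. Within this, 31.25 mcg is nominally significant in 0.804 − 0.693 = 0.111.
- 62.5 mcg significant but 31.25 mcg not: 0.804 − 0.693 = 0.111.
- Total: 0.196 + 0.111 = 0.307 = 1 − 0.693.

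Once the gate is open, the second test succeeds with probability 0.693 / 0.804 = 0.86.

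**Range (115 per arm, normal approximation).**

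| True difference, 62.5 mcg (mL) | True difference, 31.25 mcg (mL) | SD (mL) | Step-down power, 31.25 mcg |
|---|---|---|---|
| 130 | 130 | 350 | 0.69 |
| 130 | 115 | 350 | 0.62 |
| 130 | 100 | 350 | 0.53 |
| 136 | 130 | 350 | 0.72 |
| 160 | 130 | 350 | 0.77 |
| 130 | 130 | 300 | 0.84 |
| 130 | 130 | 325 | 0.77 |
| 130 | 130 | 354 | 0.68 |
| 130 | 130 | 400 | 0.55 |

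Unequal effects are assumptions. The 136 mL is the study 200699 result for 62.5 mcg. The SDs of 325 and 354 mL are the ends of the range quoted in Section 10.2, and 300 and 400 mL are the outer rows of the Section 10.3 table.

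**The case against.** The strongest reply is that Section 10.2 speaks of power for each comparison, that pairwise power is a conventional thing to report, and that the 80% is correct as such. That part stands: there is no slip in the calculation itself, and the figure holds for 62.5 mcg. It does not rescue the claim for 31.25 mcg. The sentence carries no label saying the hierarchy has been ignored, and Section 10.5.3 reduces the second p-value to description whenever the first test fails.

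Four further points are fair.
- The 11 points lost against the stated 80% are trials in which 31.25 mcg is nominally significant but the gate is closed. They are not trials in which a formal second test fails. The cost is a lost formal claim, more than a false impression that the lower dose does not work.
- No section makes success at both doses a condition for trial success, and Section 10.5.3 lets 62.5 mcg stand alone.
- There are upward scenarios: 0.72 with 62.5 mcg at 136 mL, 0.77 at 160 mL, and 0.77 with SD 325 mL. None reaches 80%. Only an SD of 300 mL does, which lies below the range quoted in Section 10.2. The SD of 400 mL belongs to a more severe population.
- Covariate adjustment and partial data in the mixed model may add power. The plan claims no such gain and sizes on the SD of the change from baseline.

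**Conclusion.** The concern holds. The stated 80% is the unadjusted power of a single comparison. For UMEC 31.25 mcg, tested as the protocol prescribes, power is about 69%, some 11 percentage points lower. This rests on true differences of 130 mL for both doses, SD 350 mL, 115 evaluable per arm and a correlation of 0.5 from the shared placebo arm. With 31.25 mcg at 130 mL and SD 350 mL, no effect of the higher dose, however large, can lift step-down power above the single-comparison value of 0.804. The power for 62.5 mcg and the control of type I error are unaffected.

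**What to change.** In Section 10.2, replace the single claim with two statements: 80% power for UMEC 62.5 mcg against placebo, and about 69% power to declare UMEC 31.25 mcg superior under the step-down procedure if both true differences are 130 mL and the SD is 350 mL. In Section 10.3, label the existing table as single-comparison power and add a row of step-down power for 31.25 mcg at true effects of 100, 115 and 130 mL (0.53, 0.62 and 0.69, with 62.5 mcg at 130 mL and SD 350 mL).

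The cost is one sentence and one table row, and a less favourable published figure. No extra participants are needed, and the hierarchy, significance level and analysis stay as they are. For information only: if the sponsor does intend 80% for both doses under the hierarchy, the same inputs require about 142 evaluable per arm, or 142 / 0.9 ≈ 158 randomized per arm and 474 in total instead of 384.

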10.3. Sample Size Sensitivity

To demonstrate the sensitivity of the sample size calculation for this study, the following table and graph show the power function for a fixed sample size of n=115 per arm in the intent to treat (ITT) population for the primary efficacy analysis, varying the true treatment difference and estimated standard deviation on the change from baseline in trough FEV₁ at the end of the 24-week treatment period.

Standard Deviation	Treatment difference (mL)				
	100	115	130	145	160
300	0.71	0.82	0.91	0.95	0.98
350	0.58	0.70	0.80	0.88	0.93
400	0.47	0.58	0.69	0.78	0.86

10.4. Sample site re-estimation or adjustment

No sample size re-estimation is planned.

10.5. Data Analysis

10.5.1. Analysis population

The following participant populations will be identified:

All Participants Enrolled Population: This population will comprise all participants for whom a record exists on the study database, including pre-screened participants that sign the informed consent document but do not complete a Visit 1 (screening) procedure (i.e., pre-screening failures), or participants that complete at least one Visit 1 procedure but do not enter the run-in period (i.e., screening failures). This population will be used for the summary of participant disposition.

All Participants Screened Population: This population contains all participants that complete at least one Visit 1 (Screening) procedure. This population will be used for the summary of participant disposition (including reasons for screening failures and run-in failures) and for the listing of AEs and SAEs for non-randomized participants.

ITT Population: This population will comprise all randomized participants, excluding those who were randomized in error. A participant who is recorded as a screen failure or

run-in failure, but is randomized and does not receive a dose of study treatment, is considered to be randomized in error. Any other participant who receives a randomization number will be considered to have been randomized. This will constitute the primary population for all efficacy and safety analyses.

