5. STUDY DESIGN

5.1. Overall Design

This is a Phase IIb, randomized, double-blind, placebo controlled, 3-arm parallel group study, comparing the efficacy, safety and tolerability of UMEC (62.5 mcg and 31.25 mcg) administered once-daily in participants with asthma that is not well controlled (i.e. participants with an ACQ-6 total score >0.75 at Visit 2 [the Randomization Visit]) despite treatment with maintenance ICS.

205832 Study – UMEC (62.5 mcg) vs UMEC (31.25 mcg) vs Placebo

Eligible participants will be requested to participate in the study for a maximum of approximately 31 weeks (Visit 0 to the Follow-up contact, inclusive) during which time, participants will complete the following 4 phases of the study:

- **Pre-screening:** Details about the study and procedures will be explained through the informed consent process. The Pre-screening Visit (Visit 0), including the informed consent process, must be completed within 4 weeks prior to Visit 1 as well as prior to any protocol-required changes to a participant's usual asthma treatment and the initiation of any Visit 1 procedures. Subjects will continue treatment with their regular (i.e. pre-study) asthma medication(s) during the pre-screening period; however, medications that are prohibited within a specified time interval prior to Visit 1 are defined in Section 7.9.

Participants that receive LABA (or LAMA) as a component of their regular (i.e. pre-study) therapy must stop LABA (or LAMA) treatment from ≥ 48 hours prior to Visit 1 (Screening) until they have completed the study; therefore, the investigator must use their clinical judgment to determine if the participant may stop LABA (or LAMA) prior to study entry without incurring undue risk.

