6.4. Pre-Screening/Screening/Run-in/Randomization Failures

A participant will be assigned a participant number at the time the informed consent is signed at Visit 0.

The study site will be responsible for reporting pre-screen failures. The following information will be collected in the eCRF for participants who are pre-screen failures:

- Demographic information including race, age and gender
- Participant number
- Serious Adverse Event information only for any SAE considered as related to study participation
- Investigator signature page

For the purposes of this study, pre-screening failures, screening failures, run-in failures and randomization failures will be defined as follows:

- **Pre-screening failures:** those participants that sign the informed consent document but do not have a Visit 1 (Screening) procedure.

- **Screening failures:** those participants that complete at least one Visit 1 (Screening) procedure but do not enter the run-in period.
A participant who completes Visit 1 assessments and is dispensed the study medication for the run-in period is considered to have entered the run-in period.
- **Run-in failures:** those participants that enter the run-in period but do not have any Visit 2 (Randomization) procedures.
- **Randomization failures:** those participants that complete at least one Visit 2 (Randomization) procedure but do not enter the double-blind study treatment period.
Any participant who completes the run-in period and then meets the randomization criteria and is dispensed the double-blind study treatment at Visit 2 is considered to have entered the treatment period.

RAMOS NG will be contacted to register the participant.

In order to ensure transparent reporting of screen/run-in failure participants, meet the Consolidated Standards of Reporting Trials (CONSORT) publishing requirements, and respond to queries from Regulatory authorities, a minimal set of screen/run-in/randomization failure information is required including demography, screen/run-in/randomization failure details, eligibility criteria, and any SAEs (see Section 9.2.4 and Appendix 4). Further details are provided in the study-specific eCRF completion guidelines document.

Re-screening of subjects will be permitted; however, advance written approval to proceed with re-screening a subject must be obtained from the Medical Monitor (for contact details, see the medical monitor/Sponsor Information Page at the beginning of this protocol).

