9.2.1. Time Period and Frequency for Collecting AE and SAE Information

- Any SAEs assessed as related to study participation (e.g., protocol-mandated procedures, invasive tests, or change in existing therapy) or related to a GSK product will be recorded from the time a participant consents to participate in the study up to and including any follow-up contact.
- AEs will be collected from the start of Study Screening until the follow-up contact (see Section 9.2.3) at the timepoints specified in the Schedule of Activities (SoA) table (Section 2).
- Medical occurrences that begin prior to the start of study treatment but after obtaining informed consent may be recorded on the Medical History/Current Medical Conditions section of the eCRF.
- All SAEs will be recorded and reported to GSK within 24 hours, as indicated in [Appendix 4](#). The investigator will submit any updated SAE data to the sponsor within 24 hours of it being available.
- Investigators are not obligated to actively seek AEs or SAEs in former study participants. However, if the Investigator learns of any SAE, including a death, at any time after a participant has been discharged from the study, and he/she considers the event reasonably related to the study treatment or study participation, the Investigator must promptly notify GSK.

NOTE: The method of recording, evaluating and assessing causality of AEs and SAEs plus procedures for completing and transmitting SAE reports to GSK are provided in [Appendix 4](#)

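### The listing of SAEs in non-randomized participants rests on a population that leaves out pre-screening failures, although their SAEs are collected from consent

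*Protocol*

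**What the plan says.** Section 10.5.1 defines three populations and states what each is for.

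- **All Participants Enrolled Population.** Everyone with a database record, "including pre-screened participants that sign the informed consent document but do not complete a Visit 1 (screening) procedure (i.e., pre-screening failures"). Its stated use: "This population will be used for the summary of participant disposition". No safety output is named for it.
- **All Participants Screened Population.** Entry depends on Visit 1: "This population contains all participants that complete at least one Visit 1 (Screening) procedure". It is used for disposition "and for the listing of AEs and SAEs for non-randomized participants".
- **ITT Population.** Randomized participants, less those randomized in error. It is the primary population for all efficacy and safety analyses.

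Section 6.4 defines pre-screening failures as "those participants that sign the informed consent document but do not have a Visit 1 (Screening) procedure". It lists SAEs considered related to study participation among the items entered in their eCRF.

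Under section 9.2.1, SAEs related to study participation ("e.g., protocol-mandated procedures, invasive tests, or change in existing therapy") or to a GSK product "will be recorded from the time a participant consents to participate in the study". The same section starts AE collection only at Screening. The Schedule of Activities agrees: SAE review is marked at Visit 0, and AE review begins at Visit 1.

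**The concern.** The collection rule and the listing rule start at different points. Collection of participation-related SAEs starts at consent, while the listing for people who were never randomized starts at the first Visit 1 procedure. The protocol therefore asks sites to record these events in pre-screening failures and then names a listing population that cannot contain those participants.

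The interval is not empty of study-driven change. Section 5.1 says that participants taking a LABA or LAMA "must stop LABA (or LAMA) treatment from ≥ 48 hours prior to Visit 1 (Screening"), and the Schedule of Activities requires consent before any medication is stopped. A change in existing therapy is one of the examples that section 9.2.1 gives of what makes an SAE participation-related. At stake is whether the study report's listing of SAEs in non-randomized participants is complete over the period in which the protocol chose to collect them.

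**Working it through.** The plan states no figure on this point, so the check is one of set membership.

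**Step 1. Where does a pre-screening failure (consented, no Visit 1 procedure) belong?**

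- Enrolled: yes, named explicitly. Stated use: disposition. Safety outputs named: 0.
- Screened: no, because the entry condition is a Visit 1 procedure. Safety outputs named: 1, the listing of AEs and SAEs in non-randomized participants, which does not reach this person.
- ITT: no, because the person was not randomized. The safety analyses named for ITT do not reach this person either.

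Safety outputs named in 10.5.1 that cover a pre-screening failure: 0 + 0 + 0 = 0.

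**Step 2. Are the other non-randomized groups covered?** Screening failures have at least one Visit 1 procedure by definition. Run-in failures and randomization failures have passed through Visit 1. All three groups are in the Screened Population, so the gap concerns pre-screening failures only.

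**Step 3. Which events are affected?** Before Visit 1 the protocol collects no non-serious AEs. It records SAEs only if they are assessed as related to study participation or to a GSK product (9.2.1). The gap is therefore limited to related SAEs between Visit 0 and Visit 1 in people who never have a Visit 1 procedure.

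**Step 4. How long is the interval?** The Schedule of Activities puts Visit 0 at Day -42 to Day -14 and Visit 1 at Day -14. The longest interval is -14 - (-42) = 28 days, which matches the limit of 4 weeks in section 5.1. For LABA/LAMA users the required time off that drug before Visit 1 is at least 48 hours, or 10 days for an indacaterol or olodaterol component (Table 3).

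**Step 5. How many events?** The documents give neither the number of pre-screening failures nor an SAE risk, so no count can be derived. For orientation only, assume 40 to 120 pre-screening failures and a related-SAE risk of 0.1% to 0.5% over the interval. These inputs are assumptions without support in the protocol. Expected events run from 40 × 0.001 = 0.04 to 120 × 0.005 = 0.6, which is less than one event in the trial across that range.

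**Step 6. Effect of the change.** With the SAE listing based on the Enrolled Population, Step 1 gives one covering output instead of none.

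**The case against.** The strongest reply is that nothing of consequence is lost. Section 9.2.1 sends every SAE to the sponsor within 24 hours, section 9.2.4 provides for onward reporting, and the event is in the eCRF. What remains is a single descriptive listing. This stands, and it sets the severity.

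A second reply is that 10.5.1 defines populations without claiming to list every output, and that matching listings to populations is ordinary analysis-plan work. Section 10.5.1 does not say that the Enrolled Population is used only for disposition. This stands in part: the gap is shown for the outputs named in that section and no further. It does not remove the point, because the protocol did not leave this listing open. It named a population, and the named one is too narrow. The deferral in section 10.6 concerns participants who withdraw prematurely from treatment or study and does not reopen this assignment.

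A reader might go further and infer that the report would selectively understate serious harm from stopping asthma maintenance treatment, because those who deteriorate most would never reach Visit 1. The documents do not support that:

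- Regular asthma medication, including ICS, continues through pre-screening. Only the morning ICS dose is withheld on the day of Visit 1. The drugs stopped before Visit 1 are LABA/LAMA and the others in Table 3, in those who take them.
- Most of the time off LABA/LAMA falls after Visit 1 (about 2 weeks of run-in and 24 weeks of treatment), where the Screened listing or the ITT Population covers SAEs.
- Appendix 4 makes it uncertain that an asthma worsening counts. Expected signs of the disease under study are not AEs unless more severe than expected, and an event that is not an AE cannot be an SAE. The same appendix includes exacerbation of a pre-existing condition among AEs, so the text points both ways.
- The protocol does not say why people become pre-screening failures. A change of mind fits the definition as well as a serious event does.

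**Conclusion.** The point holds as an internal mismatch of low severity. Section 10.5.1 ties the listing for non-randomized participants to a population that excludes pre-screening failures, while sections 6.4, 9 and 9.2.1 and the Schedule of Activities collect their participation-related SAEs from consent. Read literally, any such SAE appears in no safety output that 10.5.1 names.

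The consequence is limited to the completeness of one listing. Few or no events may be affected. Sponsor reporting is untouched, and no treatment comparison, power or alpha changes. The conclusion rests on the population definitions as written and on no assumption about event numbers. It does not extend to a claim that the trial hides or selectively understates harm.

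**What to change.** In section 10.5.1, add the listing of SAEs for non-randomized participants to the stated uses of the All Participants Enrolled Population, next to the disposition summary. Under the All Participants Screened Population, keep the listing of AEs for non-randomized participants and remove SAEs from that clause. The split follows section 9.2.1, where related SAEs are recorded from consent and AEs from Screening.

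The cost is one sentence in the protocol and one population flag in one listing. The data are already collected, so no new data, visits or participants are needed, and no clinical rule changes.
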